NVS has good reliability and validity for both English (Cronbach's alpha=0.76) and Spanish versions (Cronbach's alpha=0.69)⁶⁹ (Appendix I)

Subject recruitment

We will recruit subjects for focus groups, usability studies and the final evaluation from antenatal clinic at RWMC, Scottsbluff. The study information will be provided to the prospective subjects by the physicians and the other staff at the RWMC, Scottsbluff. Information about the study will also be disseminated through information flyers. The research staff at the College of Public Health (COPH) and College of Nursing (CON) Scottsbluff will gather data during the study months (Appendix J).

Subject eligibility

The inclusion criteria include; (1) Hispanic females age 15 years and above, (2) agreeing to participate in the study (3) telephone contact and (4) available for follow-up interview. The rationale for including 15 year old teen mothers is because Scottsbluff County has highest teen pregnancy rate in the State of Nebraska⁷⁰⁻⁷². We will include only mothers in the proposed study as the focus of the study is to analyze her attitudes, beliefs, her perceived norms towards breast-feeding; breast-feeding self-efficacy and intend to breast-feed her baby for 6 months. Subjects will be excluded if any of the following criteria are met including; (1) mental and physical challenge that makes it difficult to use the touch based computer program, (2) unavailability for telephone follow-up and (3) involvement in other clinical trials or protocols related to breast-feeding, (4) Mothers who are admitted to ICU during their hospital stay, (5) Birth weight of <2500 gms, (6) <36 weeks gestation, (7) a bilirubin >15 mg%, (8) NICU admission to provide a sample of stable infants and (9) still birth.

Data Collection procedures

Baseline data will be gathered during the enrollment prenatal visit (anytime during last six weeks of pregnancy) and follow up data will be collected on postpartum day 3, week 6 and months 3 and 6 resulting in overall five data collection time periods. The postpartum day 3 data collection will be done over the telephone while other follow up data collection including week6 and months 3 and 6 will be done when the individuals in both the groups will come to the hospital for follow up educational sessions. Almost all women who initiate breast-feeding plan to continue for at least 6 weeks; however, one of every five women quits breast-feeding within the first days after delivery⁷³. This finding supports the notion that 2–4 weeks postpartum is a vulnerable period for breast- feeding cessation⁷⁴. Baseline evaluation will be done during the prenatal visit (last trimester). The research assistant will schedule a follow up interview to administer the study questionnaires at a convenient time over the telephone. Subjects will receive gift vouchers worth \$15 for baseline and for every follow up postpartum visit (Table2).

Pre and Post educational Session data collection	Baseline	Day 3	Week 6	Month 3	Month 6
Socio-demographics	X				
Health Literacy	X				
Breast-feeding Knowledge	X	X	X	X	X
Breast-feeding self-efficacy	X	X	X	X	X
Intent to Breast-feed	X	X	X	X	X
Breast-feeding attitudes	X	X	X	X	X
Perceived norms	X	X	X	X	X
Program acceptance	X				X

Table2. Data Collection in intervention and attention control groups

Informed Consent

[name] (Consultant) is a bilingual and certified Spanish translator and will administer the informed consent and assent forms at the RWMC, Scottsbluff after the eligible subjects have agreed to participate in the study. The research staff members will read the UNMC IRB-approved consent and assent forms to subjects describing the study, the measures used by the researchers to protect the confidentiality of the responses, and the voluntary nature of the study. Those who agree to participate will be asked to sign the consent and the assent forms as appropriate. The research staff member will countersign the consent and the assent forms and copies will be given to the participant.

Data Entry and Quality Assurance

The research assistants will perform data entry and [name] (Co-Investigator) will be responsible for data management. Data will be entered into a relational database structure using Microsoft Access Forms and inconsistencies will be generated automatically by the system for verification with original forms. To ensure efficiency and high quality data collection and processing, we will have (1) well trained team of research assistants (2) clearly defined study manual (3) weekly meetings with the research staff, (4) logs of all patient contacts. To ensure efficient and accurate data management, we will (1) maintain logs of all the data instruments filled during each visit for every patient (2) central data processing and (3) weekly data checks. Minimal risks of anxiety related to filling out instruments and demographic forms may be experienced by the participants. Methods of recruitment consistent with ethical access will be used to identify patients who meet eligibility criteria and to invite them to participate in the study. All data collected will be kept confidential. Data files will be coded by number to retain the anonymity of the participants between focus groups. All data will be stored in a password protected computer in a locked office of the PI for 3 years from the point of the study completion at which time they will be destroyed. Security of the data will be maintained through regular backups, and all computers and specific data files will be password protected and kept in a locked file cabinet (Appendix K).

VII. Analysis Plan

The study will produce a very rich database consisting of a spectrum of outcome variables including the primary and secondary outcomes; it also contains information on many potential confounders and process variables. The overall objective is to investigate the impact of the intervention of using touch screen computer based breast-feeding educational support program compared to the traditional methods of informing the subjects regarding breast-feeding during their prenatal visit at the hospital. A detailed statistical analysis plan is outlined below.

Focus Group Analysis

Analysis will be systematic, sequential, verifiable, and continuous in order to minimize the potential bias introduced in analyzing and interpreting focus group data. The main source of data analysis will be the recorded spoken language. We will use Framework analysis approach as it provides a clear series of steps, which could help to manage the large amount and complex nature of qualitative data much more easily⁷⁵. The other distinctive aspect of this analysis approach is that although it uses a thematic approach, it allows themes to develop both from the research questions and from the narratives of research participants⁷⁵. The analytical process involves a number of distinct though highly interconnected stages including: familiarization; identifying a thematic framework; indexing; charting; mapping and interpretation⁷⁵.

We will conduct this analysis on the audio recorded data and the observational notes gathered during the focus group interviews. The aim will be to immerse in the details and get a sense of the interview as a whole before breaking it into parts. Themes will emerge lifting the quotes from the original context and re-arranging them under the newly-developed appropriate thematic content. One of the most important aspects of this task is data reduction, which is achieved by comparing and contrasting data and cutting and pasting similar quotes together. The data are now ready for the final stage of analysis, i.e. mapping and interpreting and prior studies have suggested the following headings as a framework for interpreting coded data: words; context; internal consistency; frequency and extensiveness of comments; specificity of comments; intensity of comments; big ideas. Computer-based approach will be employed for cutting, pasting, sorting, arranging and rearranging data through comparing and contrasting the relevant information using specialized software such as nVIVO⁷⁶.

Exploratory Data Analysis

In the first step of exploratory analysis, we will present a table to summarize the distribution of all variables, including outcomes, confounding, and process variables. This table will also serve the purpose of quality control of the original data, to mine missing data patterns and outliers. The distributions of the continuous outcomes will be explored for normality and transformations will be used if warranted. Continuous variables will be summarized using means, medians, standard deviations and ranges while categorical variables will be examined using frequencies and percentages. Exploratory analysis on process variables will be used for post-hoc analysis. Inter-rater reliability of knowledge, attitudes/beliefs, self-efficacy and intent to breast feed will be examined using the kappa statistic.

Sample Size Justification

The optimum number of participants for a focus group is typically 6-10 people with similar backgrounds who participate in the interview for one to two hours may vary⁵². The number generally suggested as being manageable is between six and ten participants as smaller groups show greater potential and large enough to gain a variety of perspectives and small enough not to become disorderly or fragmented⁵². For the intervention effect analysis, a comparison of two independent binomial proportions using Pearson's Chi-square statistic with a two-sided significance level of 0.05, a sample size of 23 per group achieves a power of at least 0.8 when the proportion with partial breast-feeding at 6 months are 0.3 for the control group and 0.7 for the intervention group. To account for anticipated attrition of 15%, the sample size will be increased to 54 subjects (27 per group). This is a pilot study to explore the possibility of promoting breast-feeding using computer based breast-feeding tailored educational program among Hispanic rural women.

Statistical Analysis

Baseline characteristics will be summarized by intervention group. A chi-square test will be used to compare baseline categorical variables between the intervention and control groups and a t-test will be used for continuous variables. The primary outcome of proportion partial or exclusive breast-feeding at 6 months will be compared between groups using a Chi-square test. The primary outcome will be assessed at 6 months; however, we will also conduct these analyses at 6 weeks and 3 months. A generalized linear mixed model using a binomial distribution and logit link function will be used to examine partial breast-feeding at day 3, week 6 and months 3 and 6 postpartum, with intervention group as a fixed effect and subject as a random effect using a Variance Components covariance structure. In exploratory analyses, covariates will be added to the model to adjust for confounders that differ significantly between both the intervention and attention control groups at the 0.20 level of significance. Similar analyses will be conducted to examine exclusive breast-feeding. Breast-feeding knowledge, self-efficacy, will be compared between groups using a t-test. In exploratory analyses, a general linear mixed model with intervention group as a fixed effect and subject as a random effect using an AR (1) covariance structure will be examined. Covariates will be added to the model to adjust for confounders that differ significantly between both the intervention and attention control groups at the 0.20 level of significance (Table3).

Variables Assessment	Variable types	Data Analysis	Anticipated Outcomes
Focus groups	Qualitative	Framework analysis	Breast-feeding educational modules and functionality of the computer based program established
Socio-Demographics	Continuous & Categorical	T test for continuous and Chi-square tests for categorical variables.	Distribution of population characteristics
Intent to Breast-feed	Categorical	Chi-Square test	Assess intent to breast-feed

Breast-feeding knowledge	Continuous	T test	Improve Breast-feeding knowledge (intervention)
Breast-feeding attitudes and beliefs	Continuous and categorical	T test for continuous and Chi-square tests for categorical variables.	Change Breast-feeding related attitudes and beliefs
Breast-feeding perceived norms	Continuous and categorical	T test for continuous and Chi-square tests for categorical variables.	Change Breast-feeding related behavior
Breast-feeding self-efficacy	Continuous	T test	Improve self-efficacy (intervention)
Breast-feeding assessment	Categorical	Chi-square test	Better breast-feeding practices (intervention)

Table3. Analysis Plan

VII. Project Timelines and Milestones

The research plan entails the performance of the following tasks: (a) Modify and enhance the PEMT to deliver breast-feeding education to the Hispanic rural women about major topics such as: review the benefits of breast-feeding, principles of lactation, myths, common problems, solutions and skills training appear to have the greatest effect, (b) deliver education tailored to individual profiles including demographics age and health literacy, (c) Other variable information gathered will include breast-feeding knowledge, attitudes and practices, (d) implement tailoring strategies, (e) assess the impact on the study outcomes and (f) perform data analysis and report the results. The Research investigators will coordinate a meeting once every month. The meeting points will be mailed to the members of the research team 72 hours before the meeting so that enough time is available to review and provide appropriate suggestions as needed. The research analysts will be responsible for the overall coordination of the meetings. The timeline of the study has been presented in the Table below (Table4).

Tasks involved	Timeline	Objectives
Research Team meet	Month 1	To formulate and strategize the study implementation plan
Focus group and Analysis	Months 2&3	Identify relevant breast-feeding educational modules
Breast-feeding Educational Content developed (English and Spanish)	Months 3-5	Develop breast-feeding educational modules based on initial findings of the focus group and investigators' expert opinion.
Modify existing PEMT	Months 5-6	Modify and integrate the breast-feeding educational modules into a computer format
Computer program redesign using heuristic principles	Months 5-6	Modify and integrate the breast-feeding educational modules into a computer format
User testing	Months 6	Usability evaluation of the system
System deployment	Months 7	System modified based on users feedback and final deployment of the computer program
Subject Recruitment	Months 8 to 13	Subject Enrollment initiated

Data Collection	Months 8-20	Baseline and follow up data collection
Analysis and Results	Month 6, 12, 20	Data entry, data analysis and initial findings reported
Dissemination	Month 6, 12, 18, 24	Final study findings disseminated to the funding and other key agencies

Table4. Project Timeline

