- **Usability and User testing:** We will recruit six Spanish speaking pregnant Hispanic rural women at the RWMC, Scottsbluff to interact with the system. They will be enrolled at the Regional West Medical Center (RWMC), Scottsbluff, NE. [name] and [name] (Consultant) will be responsible for subject recruitment. Information flyers will be available at the RWMC to inform the subjects about the study. These subjects will not be part of the actual study. After a brief introduction to the system, study subjects will be asked to complete a predefined set of tasks by interacting with the system and the duration of this interaction will be around 30 minutes. We will have a think aloud protocol that will involve participants thinking aloud as they perform a set of specified tasks. Users will be asked to say whatever they are looking at, thinking, doing, and feeling, as they go about their task. This will enable observers to see first-hand the process of task completion. Notes and test sessions will be audio taped of everything that users' say, without attempting to interpret their actions and words will be taken. During these assessments, we will gather basic quantitative results including information about the time required to complete tasks and the errors encountered using the usage data metrics as described previously (Section II. Conceptual framework). A likert scale survey will be used to assess user satisfaction with the computer program and any recommendations study subjects may have to improve the system. The results of the user testing will be followed by incorporating the recommended changes to the design of the Computer-based Breast-feeding educational support program during months 6 and 7. The final program will be deployed during month 8 of the study period.

IV. Research Design and Methods

The proposed pilot study is a two-group repeated measures quasi-experimental design that will be used to explore the effect of using Computer based Breast-feeding Educational Support program to promote breast-feeding in rural Hispanic women. (Figure4)

Control	Confounders	Primary Outcome
	Socio-demographics Breast-feeding status	Partial or Exclusive Breast-feeding till six months (Proportion)

[figure not shown]
[figure not shown]

Figure4.Research Design

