The subjects will be enrolled at RWMC, Scottsbluff and randomly assigned to either intervention (bilingual Computer based Breast-feeding Educational Support program) or attention control (bilingual breast-feeding printed educational material) groups during the subject's prenatal visit (i.e. anytime during last six weeks of their pregnancy). Once randomized, baseline information will be gathered in both the groups as outlined in Figure5. The difference between the two study groups is that subjects in the intervention (bilingual Computer based Breast-feeding Educational Support program) will record their baseline assessment on a computer and receive tailored breast-feeding education compared to the attention control (bilingual printed breast-feeding educational materials) who will record their baseline information on paper (Figure5) and receive printed breast-feeding educational material. Using self report responses of the individuals in the intervention group (bilingual computer based breast-feeding educational support program), the decision logic and algorithm will process the information and deliver tailored breast-feeding educational messages in varied multimedia formats using a combination of text, images, and animations to account for the literacy levels of the subjects. Appropriate feedback will be given in the form of reinforced educational messages and encouragement and motivational prompts for those using the computer based program. Educational session in both the groups will last for 30 minutes. The first educational session will be performed during the post partum period, one day before the discharge from the hospital followed by week 6, months 3 and 6. Specific individualized interventions, especially during the initial critical 2-6 week period, are needed to prevent deterioration in intention levels for breast-feeding for 6 months and breast-feeding self-efficacy levels within the first 2 weeks postpartum which could lead to the decision to discontinue breast-feeding³¹. Subjects in both the groups will be given telephone reminders for follow up educational sessions. The touch screen computer based Breast-feeding Educational Support program will be placed on a mobile cart in the outpatient clinic of the RWMC, Scottsbluff. A research assistant will be available to guide the subjects in both the intervention (during the use of the tablet pc program) and the control groups (printed educational material) if needed. The breast-feeding educational modules and data collection instruments will be both in English and Spanish.

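### The study is labelled quasi-experimental although women are randomised, and the primary month-6 chi-square makes no use of previous breast-feeding, which the trial already records

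*Combined protocol and SAP*

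**What the plan says.** The opening of section IV reads: "The proposed pilot study is a two-group repeated measures quasi-experimental design". The following paragraph says: "The subjects will be enrolled at RWMC, Scottsbluff and randomly assigned to either intervention" or attention control, at a prenatal visit in the last six weeks of pregnancy. It continues: "Once randomized, baseline information will be gathered in both the groups as outlined in Figure5". Nothing in the text reconciles the two descriptions.

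Sample Size Justification rests on "a comparison of two independent binomial proportions using Pearson's Chi-square statistic with a two-sided significance level of 0.05". It says that "a sample size of 23 per group achieves a power of at least 0.8" for rates of 0.3 (control) and 0.7 (intervention), and raises the total to 54 (27 per group) for 15% attrition.

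Potential Confounders (section IV, item d) includes previous history of breast-feeding among the socio-demographic items. Table 2 schedules those items at baseline. Under Statistical Analysis, the primary proportion at 6 months is compared by chi-square with no covariate. Covariates enter only in exploratory mixed models, and only if they differ between groups at the 0.20 level.

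**The concern.** There are two linked problems.

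The first is the label. The Analysis Plan's overall objective is the impact of the program against traditional education, and the background presents the study as the foundation for a multicentre randomised trial. With random allocation, the month-6 difference supports a causal reading. Without it, an unadjusted chi-square is open to confounding. A reader who meets the design sentence first would draw the second conclusion about a study whose procedure supports the first.

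The second is precision. With 23 to 27 women per arm, each woman is about 4 points of the primary proportion. Whether a mother has breast-fed before is plausibly related to whether she is still breast-feeding at 6 months, and the protocol itself treats it as a confounder. The primary test ignores it. The adjustment that does exist sits outside the primary analysis and is triggered by a baseline significance test, which measures imbalance and not how strongly the factor predicts outcome.

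**Working it through.** **Design statements side by side.** Label: quasi-experimental (section IV, first sentence). Procedure: random assignment, stated once and then presupposed by the word randomized (section IV, second paragraph). Planned arms: equal (Sample Size Justification). No text describes a non-random way of forming groups. Every operative statement points to randomisation, and only the label does not.

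**Reproducing the plan's sample size.** Inputs: 0.3, 0.7, two-sided 0.05, power 0.8.
- n = [1.96 × √(2 × 0.5 × 0.5) + 0.842 × √(0.21 + 0.21)]² / 0.40² = 23.3 per group, or 24 when rounded up.
- Exact enumeration of the uncorrected Pearson chi-square at 23 per group gives power 0.809, so the claim of at least 0.8 holds.
- Attrition: 46 / 0.85 = 54.1, against 54 planned.
- At 27 per group, power is 0.857 by normal approximation and 0.840 exactly.

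**Precision available from previous breast-feeding.** Assumptions, because the documents give no figures: half the women have breast-fed before, and they are 30 points more likely to continue. Rates are then 0.15 and 0.45 in control and 0.55 and 0.85 in intervention, which average to the plan's 0.3 and 0.7.
- Per-woman variance ignoring the factor: 0.3 × 0.7 = 0.21 in each arm.
- Within strata: (0.15 × 0.85 + 0.45 × 0.55) / 2 = (0.1275 + 0.2475) / 2 = 0.1875, and the same in the intervention arm.
- Reduction: (0.21 − 0.1875) / 0.21 = 10.7%.
- Standard error at 27 per arm: √(2 × 0.21 / 27) = 0.125 falls to √(2 × 0.1875 / 27) = 0.118.
- This is worth 0.21 / 0.1875 = 1.12, or about 12% more women.

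**Simulated rejection rates** (400,000 trials per row, equal arms, two-sided 0.05, no continuity correction, prevalence 50%):

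| Scenario | Per arm | Plain chi-square | Cochran-Mantel-Haenszel |
|---|---|---|---|
| 0.3 v 0.7, 30-point factor effect | 27 | 0.840 | 0.889 |
| Same | 23 | 0.810 | 0.834 |
| 0.3 v 0.7, 20-point factor effect | 27 | 0.840 | 0.866 |
| Same | 23 | 0.810 | 0.809 |
| 0.3 v 0.7, no factor effect | 27 | 0.840 | 0.845 |
| Same | 23 | 0.809 | 0.792 |
| No treatment difference (0.3 in both), 30-point factor effect | 27 | 0.055 | 0.049 |
| Same | 23 | 0.050 | 0.049 |

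Part of the row-to-row variation comes from the discreteness of the plain test at these sizes. The gain ranges from nil to about 5 points, and the largest loss is 0.809 − 0.792 = 1.7 points. Both tests hold the 5% level to within about half a point.

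**The case against.** The strongest reply is that this is a pilot with one mistaken word. Random assignment is stated plainly, so the label changes nothing about how women are allocated. The plan also already adjusts for imbalance. With 27 per arm, a gap of 20 points or more in previous breast-feeding means at least 6 women, and every such minimum split gives p of at most 0.10 (uncorrected chi-square) or 0.17 (continuity-corrected or Fisher). It would therefore trigger the 0.20 rule. Much of this stands: the label is a mislabel and not evidence of non-random allocation, and the exploratory models do respond to large imbalances. They do not alter the primary comparison, however, and they leave out a strong predictor that happens to be balanced, where adjustment still gains precision.

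A reader might infer three stronger points, which the documents do not support.

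- **The chi-square is invalid because chance imbalance can move the result.** At 27 per arm, a factor with 50% prevalence differs by 20 points or more in 13% of allocations (10% at 30% prevalence). A 20-point gap with a 30-point effect shifts the difference by 0.20 × 0.30 = 6 points. Under randomisation that shift goes in either direction and is part of the sampling variation that the test covers. The null rejection rates above confirm this.
- **Random assignment will seldom give 27 per group.** Simple randomisation of 54 would give exactly 27/27 in 10.8% of trials and 23/31 or worse in 34.1%. The plan does not say that assignment is simple. The cost is also small: by normal approximation, power is 0.857 at 27/27 and 0.846 at 22/32. With 46 evaluable women, average power is 0.786 against 0.794 at 23/23.
- **The study may in fact be non-randomised.** No text describes such an allocation.

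**Conclusion.** The point holds in two parts. The label contradicts the stated procedure and must be reconciled with it. This rests on the text alone and needs no assumption. The primary analysis is valid under randomisation but less precise than it could be at almost no cost. That part depends on how prognostic previous breast-feeding is, which the documents do not quantify. With a 30-point effect and 50% prevalence, the gain is about 5 points of power at 27 per arm and 2 at 23. With a 20-point effect, it is about 3 points at 27 per arm and nil at 23. With no effect, the worst case is a loss of about 2 points. This is an improvement worth pre-specifying, not the correction of an invalid test. The number of women in each arm is not a ground for the change.

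**What to change.** 1. In section IV, delete quasi-experimental and describe a two-arm, 1:1, individually randomised pilot with repeated measures.
2. Under Statistical Analysis, make the primary month-6 comparison a Cochran-Mantel-Haenszel test with a stratified risk difference and confidence interval on previous breast-feeding (yes/no, with first-time mothers counted as no). Keep the plain chi-square as a sensitivity analysis. Fix this covariate in advance, whatever the baseline test shows, and change Table 3 to match.
3. If that one question can be asked before assignment, stratify a blocked, concealed allocation list by it. State who generates and holds the list.

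The stratified analysis does not depend on item 3, because previous breast-feeding is settled before enrolment. Asking first is still preferable, since the two groups record baseline data by different means (computer or paper).

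Cost: a wording change, one question moved ahead of assignment, two short block lists in place of one, and at most about 2 points of power if the factor proves not to be prognostic. No extra women or visits are needed.
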